1.19 HEALTH ECONOMIC OUTCOMES

1. Health-related quality of life will be captured using European Quality of Life 5 Dimensions 5 Level Version (EQ-5D-5L) questionnaire. 2. Healthcare resource use and productivity loss will be captured using a bespoke resource questionnaire. The outcomes will be collected at baseline, 3 months, 6 months, 12 months and then annually to the end of trial follow-up.

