In trials of PCI versus CABG that have enrolled patients with preserved left ventricular (LV) systolic function, early outcomes typically favour PCI because it is much less invasive, results in substantially less organ injury, and allows much more rapid recovery. In contrast, the superior patency of coronary grafts over stents in conditions that increase the likelihood of stent failure; extensive multivessel or left main stem disease, or diabetes, favour CABG in the long-term. In patients with long-term conditions or frailty, the point at which the balance of early risk outweighs the later benefits for CABG is often a matter of judgement. These situations require multidisciplinary team (MDT) Heart Team discussion that includes assessment of surgical risk. In the UK, this is provided by EuroSCORE II. However, multiple additional considerations are included in these discussions for which there is no high-quality evidence:

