1.20 FOLLOW-UP

Patients will be followed up during their index hospital stay (or stays for planned staged PCI). Primary and secondary outcome measurements will be collected for a minimum follow-up of 4 years and given a 41-month recruitment period will result in a median follow-up length of 5.3 years. Outcome measurements during follow-up (excluding PROMS and 30-day SAEs) will be determined through routinely collected HES/ONS data.

Quality of Life Assessments, and Health Economic Outcomes will be ascertained at baseline, and then using telephone follow-up or self-completion using the ResearchApp™ (Healthbit®) at 3 months, 6 months, 12 months and then annually post randomisation (\pm 28 days) until the end of trial follow-up. Please refer to **Table 1** for further details about follow up visits.

Consent for life-long trial follow-up following completion of this trial's current funded period (i.e., beyond 41 months recruitment + 48 months follow-up period) using routinely collected healthcare data will be obtained.

Consent will be sought for relatives/friends to provide information if and when it is established that the participant is not contactable, has lost capacity or is too unwell, to ascertain what has happened to them. Where available and willing, two alternate contacts should be sought, through the means of the Consent to Contact Form. If it is subsequently determined that the participant has lost capacity or has become too unwell to respond to follow-ups, the research teams will initially attempt contact with the named relative(s)/friend(s) to seek consent using the Personal Consultee Information Sheet, which they may be provided with in advance, and Personal Consultee Declaration form, which can only be signed in the event that the participant has lost capacity. We will also seek consent to notify their general practitioner (GP) of their participation of their participation in the trial.

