1.27 ALLOCATED TREATMENT

Revascularisation appropriateness and feasibility will be confirmed by the local Heart Team (a minimum of an interventional cardiologist and a cardiac surgeon). Revascularisation should be performed as soon as dictated by clinical urgency but no more than 18 weeks (+/- 28 days) from randomisation for elective cases or 6 weeks from randomisation for urgent/ACS cases (+/- 28 days).

Complete revascularisation of all viable myocardium is the goal for all patients. Revascularisation will be attempted on/for significant lesions in major coronary vessels/side branches as planned by the local Heart Team, with the general recommendation of stenotic/occluded vessels with diameter >1.5mm. As per contemporary ESC treatment guidelines, physiological or non-invasive functional confirmation of haemodynamic severity should be sought in any vessel that has <90% stenosis. As a measure of process, and to estimate completeness of revascularisation, the British Cardiovascular Intervention Society Jeopardy Score (BCIS-JS) will be calculated at baseline and after final stage PCI or CABG using the www.BCIS-JS.com calculator.

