1.27.5 Duration of the Intervention

Revascularisation will be completed as per institutional norms after consideration of presentation, access to care, and resources. In ACS, revascularisation should be encouraged to be undertaken during the index admission but patients may be discharged to return for PCI or CABG. If this is the case, revascularisation should be undertaken as soon as dictated by clinical urgency but no more than 6 weeks (+/- 28 days) of randomisation. For non-ACS cases, the assigned treatment should be undertaken as soon as possible after randomisation and no more than 18 weeks (+/- 28 days) later.

Table 1 Schedule of Processes

Assessment	Screening	Baseline Assessment	Index Procedure	Post Procedure until Discharge	3 Months	6 Months ¹	12 Months ¹	6 Months and every 6 Months to 4 Years	Every 12 months to 4 Years ¹	Following LPLV
	-90 to 0	-30 to 0	Day 0	Day of revascularisation procedure until hospital discharge	+/- 28 days after Day 0	+/- 28 days after Day 0	+/- 28 days after Day 0	6 months +/- 28 days after Day 0	+/- 28 days after Day 0	
Informed Consent	X									
Inclusion/Exclusion	X									
Revascularisation and feasibility confirmed by local Heart Team	X									
Pregnancy Test ²	X ²									
Demographics, Height and Weight		X								
Medical/Cardiac History (including long term conditions and severity of cardiac diseases)		X								
Risk Scores (BCIS Myocardial Jeopardy Score and EuroSCORE II)		X		X						
Randomisation		X								
NYHA Class and CCS Class		X		X	X			X		
Kansas City Cardiomyopathy Questionnaire (KCCQ)		X		X	X			X		

Assessment	Screening	Baseline Assessment	Index Procedure	Post Procedure until Discharge	3 Months	6 Months ¹	12 Months ¹	6 Months and every 6 Months to 4 Years	Every 12 months to 4 Years ¹	Following LPLV
	Visit window (days) (± number of days this visit can take place ahead or after its due date)	-90 to 0	-30 to 0	Day 0	Day of revascularisation procedure until hospital discharge	+/- 28 days after Day 0	+/- 28 days after Day 0	+/- 28 days after Day 0	6 months +/- 28 days after Day 0	+/- 28 days after Day 0
Seattle Angina Questionnaire 7 (SAQ-7)		X		X	X			X		
EQ-5D-5L		X ¹			X ¹	X ¹	X ¹		X ¹	
Health Care Resource Use		X ¹			X ¹	X ¹	X ¹		X ¹	
Revascularisation procedures and revascularisation completeness			X							
Procedural Data Collection				X						
Concomitant Medications ³		X ³	X ³	X ³	X ³			X ³		
Clinical Events ⁴			XXXXXXXXXXXXXXXXX ⁴							

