HES codes for all pre-specified clinical outcomes, severe adverse events of interest will be specified in the Statistical Analysis Plan (SAP).

5. Disease-specific PROMS, including the clinical summary scores of the Kansas City Cardiomyopathy Questionnaire (KCCQ) and the overall summary scores of the Seattle Angina Questionnaire-7 (SAQ-7) will be ascertained at baseline and discharge, and then at follow-ups at 3 months, 6 months, and every 6 months thereafter using telephone / ResearchApp™ (Healthbit®). Where related to baseline, relevant measures will be performed after consent and prior to randomisation.
6. Resource use data, productivity loss, and EQ-5D-5L will be captured at baseline, and thereafter at 3, 6 and 12 months and then annually thereafter. Participants will have the option of either remote data capture using the Participant Portal to ResearchApp™ (Healthbit®), or if preferred, the Investigator Portal with research staff in person during enrolment and hospital stay, or by post or telephone follow-up post discharge in survivors identified from NHS SPINE.

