We will conduct the evaluation alongside the clinical trial over a minimum 4-year time horizon and a model-based evaluation over a lifetime horizon. We will capture all healthcare resource use utilised in both treatment groups over the duration of the trial. This will include resource use relating to treatment received (CABG and PCI), hospitalisations, cardiac outpatient visits and both paid and unpaid care received by the patient during follow-up. Hospitalisation data will be obtained from HES (as detailed in section 1.35). We will take key components of the iPCQ questionnaire relating to productivity and include these in the bespoke health resource use questionnaire. A focus group of National Cardiac Surgery PPI group members, led by our PPI co-applicants, identified the impact that HF can have on formal and informal carers as highly important. Therefore, the burden on formal and informal carers needs to be measured and incorporated in the health economic evaluation. Healthcare resource usage that is not captured by HES will be collected via a bespoke questionnaire, completed at baseline, three, six and twelve months and then annually thereafter until year four. For the within-trials analysis, mean total patient cost by trial arm will be estimated by applying national unit costs to healthcare resource use data. Health-related quality of life will be captured using the EQ-5D-5L questionnaire. EQ-5D-5L results will be mapped on to the EQ-5D-3L system using a “crosswalk” algorithm (36). Quality-adjusted life years (QALYs) gained will be estimated using the baseline-adjusted area under the curve approach (37). Where missing data are encountered, we will explore the assumptions regarding the missing data mechanism and decide upon an imputation method based on best practice (38). The mean total cost and mean total QALY gain per patient, according to randomisation group, will be estimated using a generalised linear model (GLM) and adjusting for trial minimisation factors and potential confounding factors. The appropriate family for GLM will be selected based on the results of the modified Park’s test. Cost-effectiveness at year four will be expressed as the incremental cost-effectiveness ratio (ICER) and net monetary benefit (NMB). We will assume a willingness-to-pay for QALY gains of £20,000. We will undertake probabilistic sensitivity analysis to explore the uncertainty in our results and plot the probability of cost-effectiveness on the cost-effectiveness acceptability curve (39). We will also undertake sensitivity analysis to explore the impact of our assumptions made regarding missing data by including a complete case analysis only. The impact of decision maker perspective will also be

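### EQ-5D-5L is not scheduled between baseline and 3 months, so the area-under-the-curve QALY mis-measures early recovery, in a direction that depends on an unreconciled time zero

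*Protocol*

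**What the plan says.** Section 1.19 sets the health-economic schedule: "The outcomes will be collected at baseline, 3 months, 6 months, 12 months and then annually to the end of trial follow-up". Section 1.31 item 6 repeats it: "Resource use data, productivity loss, and EQ-5D-5L will be captured at baseline, and thereafter at 3, 6 and 12 months and then annually thereafter". Table 1 agrees and marks no EQ-5D-5L in the column running from the procedure to discharge.

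The disease-specific questionnaires do have an early reading. Section 1.31 item 5 says that KCCQ and SAQ-7 "will be ascertained at baseline and discharge, and then at follow-ups at 3 months", and Table 1 marks both before discharge.

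The Health Economic Evaluation section says that QALYs "will be estimated using the baseline-adjusted area under the curve approach", valued at £20,000 each.

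Three other places bear on the point:

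- **Time zero.** Section 1.20 places these assessments "at 3 months, 6 months, 12 months and then annually post randomisation". Table 1 counts visits from Day 0, which is its index-procedure column; one column reads "6 months +/- 28 days after Day 0".
- **Wait for the procedure.** Section 1.27 allows revascularisation "no more than 18 weeks (+/- 28 days) from randomisation for elective cases", and 6 weeks with the same tolerance for urgent cases.
- **Early surveys.** Section 1.37 describes quality-of-life surveys prompted through the app at 4 weeks post-operation, or by interview at 6 weeks. It does not name the instrument, and neither time appears in Table 1, 1.19 or 1.31.

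**The concern.** Cost-effectiveness is a stated objective, and the Rationale notes that quality of life has not been studied for this comparison. It also says that "early outcomes typically favour PCI because it is much less invasive, results in substantially less organ injury, and allows much more rapid recovery". That sentence concerns trials in patients with preserved left ventricular function, but nothing in the protocol suggests that recovery from surgery is quicker when function is poor.

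An area under the curve, read in the usual way as straight lines between readings, sees only what the readings see. A dip that starts and ends between two readings counts as zero. A dip caught by one reading is spread over the whole interval on either side of it and can count for more than it was. Which of these happens depends on when the visit falls relative to the procedure, and the protocol gives two answers to that. At stake is an error in incremental QALYs, and so in the ICER and net monetary benefit, that comes from the timetable rather than from the treatments.

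**Working it through.** The protocol gives no QALY figure to reproduce.

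**Inputs from the protocol.** Readings at 0, 3, 6 and 12 months (0, 13.04, 26.09 and 52.18 weeks); £20,000 per QALY; longest elective wait 18 weeks = 126 days, or 126 + 28 = 154 days (22 weeks) with the tolerance; longest urgent wait 42 + 28 = 70 days (10 weeks).

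**Assumptions, not in the protocol.** After CABG, utility drops by D and recovers linearly over R weeks, with D from 0.1 to 0.3 and R from 6 to 12. After PCI, a drop of 0.05 over 2 weeks. No later gain unless stated.

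**1. Visits timed from the procedure (Table 1).** Recovery is complete before the 3-month reading, so the missed area is 0.5 × D × R / 52.18.

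| D | R (weeks) | CABG QALYs overstated by | At £20,000 |
|---|---|---|---|
| 0.1 | 6 | 0.0057 | £115 |
| 0.2 | 8 | 0.0153 | £307 |
| 0.2 | 12 | 0.0230 | £460 |
| 0.3 | 12 | 0.0345 | £690 |

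The PCI dip misses 0.5 × 0.05 × 2 / 52.18 = 0.001. For D = 0.2 and R = 8 to 12, the error in CABG minus PCI is therefore +0.014 to +0.022. With a later gain of 0.10 in both arms it is +0.020 to +0.032.

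**2. Visits timed from randomisation (section 1.20).** Take a 10-week wait, D = 0.2, R = 8.

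- The 3-month reading falls 13.04 − 10 = 3.04 weeks after surgery, with 0.2 × (1 − 3.04/8) = 0.124 of the dip left.
- Straight lines from week 0 to week 13.04 to week 26.09 record a loss of 0.5 × 0.124 × 26.09 / 52.18 = 0.0310.
- The true loss is 0.5 × 0.2 × 8 / 52.18 = 0.0153.
- CABG's QALYs are understated by 0.0157.

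The same calculation at other waits gives this error in CABG minus PCI (D = 0.2, no later gain):

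| Wait (weeks) | R = 8 | R = 12 |
|---|---|---|
| 0 | +0.014 | +0.022 |
| 6 | +0.008 | +0.001 |
| 10 | −0.017 | −0.015 |
| 12 | −0.023 | −0.018 |
| 14 | +0.014 | +0.022 |
| 18 | +0.014 | −0.002 |
| 22 | −0.022 | −0.027 |

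At 14 weeks and beyond, the 3-month reading precedes surgery. With a later gain of 0.10 and waits spread evenly over 0 to 18 weeks, the average error is about +0.005 to +0.006; over 0 to 22 weeks it is about 0.000 to +0.003.

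**3. What an added reading does** (procedure at Day 0, D = 0.2, discharge assumed at 1 week). Remaining error in CABG QALYs:

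| Added EQ-5D-5L | R = 6 | R = 8 | R = 12 |
|---|---|---|---|
| None | +0.0115 | +0.0153 | +0.0230 |
| 4 weeks only | +0.0032 | +0.0028 | +0.0063 |
| 6 weeks only | +0.0115 | +0.0091 | +0.0105 |
| Discharge only | −0.0093 | −0.0065 | +0.0001 |
| Discharge and 6 weeks | +0.0019 | −0.0005 | +0.0009 |

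Discharge alone overcorrects when recovery is quick. For R = 6 the reading is 0.2 × 5/6 = 0.167 below baseline, and the line to 13.04 weeks records 0.5 × 0.167 × 13.04 / 52.18 = 0.0208 against a true 0.0115.

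**4. Using the procedure date.** In the 10-week example, holding baseline utility to week 10 reduces the recorded loss to 0.5 × 0.124 × (26.09 − 10) / 52.18 = 0.0191. The error shrinks from −0.0157 to 0.0153 − 0.0191 = −0.0038.

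**The case against.** A reader might infer from the schedule that the area always favours CABG. The documents do not support that: it is true of the dips tested on Table 1's clock, but on section 1.20's clock the sign reverses at several permitted waits, and the average error is small.

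The loss is also not always wholly missed on Table 1's clock. The 3-month window is ± 28 days. A reading at 9 weeks during a 12-week recovery still finds a quarter of the dip, and the lines out to 26 weeks record 0.5 × 0.25 × 26 = 3.25 of the true 0.5 × 12 = 6 dip-weeks. For D = 0.2 the overstatement is then 0.2 × 2.75 / 52.18 = 0.0105 instead of 0.0230.

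Section 1.37 may intend EQ-5D-5L at 4 or 6 weeks. That would help, but with no instrument named, a time that differs by mode of contact, and no entry in Table 1, it cannot be relied on.

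KCCQ and SAQ-7 at discharge, days alive and out of hospital at 90 days, and hospital costs from HES cover parts of early recovery, but none supplies a utility for the QALY.

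The size rests entirely on assumed dips. With no incremental QALY or cost in the protocol, nobody can show that the cost-effectiveness conclusion would change. This objection stands. Nor should one infer that the error passes into the lifetime model: that section describes health states, extrapolated clinical outcomes and literature-based parameters, and does not say that within-trial QALYs feed in.

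**Conclusion.** The gap is real and belongs to the protocol. The schedule has no EQ-5D-5L reading tied to early recovery, although two other questionnaires are taken at discharge, and what is not collected cannot be restored in analysis.

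On Table 1's clock, CABG's QALYs are overstated by about 0.006 to 0.034 per patient (£115 to £690) for the assumed dips with no later gain and a 3-month reading taken after recovery. On section 1.20's clock, no single direction can be claimed: for D = 0.2 with no later gain, the error in CABG minus PCI ran from −0.027 to +0.022 across the waits tested. Straight-line interpolation is the usual meaning of area under the curve, but the protocol does not state it. The point merits a schedule change because the change is cheap, not because a wrong conclusion has been shown.

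**What to change.** 1. Reconcile the time zero of follow-up in section 1.20 with Day 0 in Table 1. Reconcile the 4- and 6-week surveys in section 1.37 with Table 1, naming the instruments.
2. In Table 1, section 1.19 and section 1.31 item 6, add EQ-5D-5L at one fixed early post-procedure contact, the same for both arms, at about 4 to 6 weeks and using the contact that section 1.37 already describes. Add it also at discharge, where KCCQ and SAQ-7 are already collected, but not at discharge alone.
3. Calculate the QALY area from actual assessment and procedure dates, holding the pre-procedure utility up to the procedure date. As the 10-week example shows, this reduces the error on the randomisation clock but does not remove it, so steps 1 and 2 are still needed.

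The cost is a schedule amendment and one or two extra completions of a short questionnaire per participant, at contacts already held or described.

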1.20 FOLLOW-UP

Patients will be followed up during their index hospital stay (or stays for planned staged PCI). Primary and secondary outcome measurements will be collected for a minimum follow-up of 4 years and given a 41-month recruitment period will result in a median follow-up length of 5.3 years. Outcome measurements during follow-up (excluding PROMS and 30-day SAEs) will be determined through routinely collected HES/ONS data.

Quality of Life Assessments, and Health Economic Outcomes will be ascertained at baseline, and then using telephone follow-up or self-completion using the ResearchApp™ (Healthbit®) at 3 months, 6 months, 12 months and then annually post randomisation (\pm 28 days) until the end of trial follow-up. Please refer to **Table 1** for further details about follow up visits.

Consent for life-long trial follow-up following completion of this trial's current funded period (i.e., beyond 41 months recruitment + 48 months follow-up period) using routinely collected healthcare data will be obtained.

Consent will be sought for relatives/friends to provide information if and when it is established that the participant is not contactable, has lost capacity or is too unwell, to ascertain what has happened to them. Where available and willing, two alternate contacts should be sought, through the means of the Consent to Contact Form. If it is subsequently determined that the participant has lost capacity or has become too unwell to respond to follow-ups, the research teams will initially attempt contact with the named relative(s)/friend(s) to seek consent using the Personal Consultee Information Sheet, which they may be provided with in advance, and Personal Consultee Declaration form, which can only be signed in the event that the participant has lost capacity. We will also seek consent to notify their general practitioner (GP) of their participation of their participation in the trial.

1.21 END OF TRIAL

For an individual participant, the end of trial is defined as time of last follow-up visit (4 years post randomisation), participant withdrawal, or mortality, whichever occurs sooner.

Participants will be considered lost to follow-up if there is insufficient information or inability to gather necessary data points required for the trial, although this is expected to be anomalous as data points are routinely collected in standard practice. In the instance where it is not possible to obtain follow-up data for one particular point in time (e.g., 6-month follow-up) the participant should not be considered as lost to follow-up at this point but rather the next follow-up in sequence should be attempted at the relevant time point within the stipulated window (e.g., 12 months). This process should be followed up until the last follow-up visit at which point if no further follow-ups have been completed from timepoint X, then the participant should be considered as lost to follow-up from that timepoint. This should not prevent the performance of NHS Digital (or equivalent) extractions, unless an explicit withdrawal from this element of the trial is communicated.

The length of time covered by routinely collected data extractions will depend on the point at which the participant consented to participation in the trial. For example, a participant recruited early on in the recruitment phase (months 5 – 45) will have more routinely collected data collected until last patient last visit (LPLV) (month 93) than a participant recruited later on in the trial.

On the whole, the definition of end of the trial is the final data lock following any data query resolutions (months 94 – 97, or approximately 8 years). Following this, participants will be informed of the trial study result should they have explicitly requested this by way of informed consent, thus being reflected on the ICF. This will be performed by each recruiting site.

TRIAL PROCEDURES

1.22 SCREENING

Sites will be responsible for ensuring that participants have provided informed consent and that this is recorded in a data secure manner. Before revascularisation, non-identifiable, non-personal data will be collected electronically by the research staff at each site on screening forms recording trial eligibility and consent rates. Specific screening requirements, including laboratory or diagnostic testing, are not required. Details of all participants approached for the trial and reasons for non-participation (e.g., reasons for being ineligible or refusal where provided) will be documented.

